2.5 DATA HANDLING CONVENTIONS

This section describes general rules for data handling conventions, especially for patients with missing data.

2.5.1 General conventions

The following formulas will be used for computation of parameters.

Reference day

The reference day for the calculation of extent of exposure, time to onset and relative days is the day of the first administration of open-label IMP, denoted as Day 1.

Disease characteristics formulas

Duration of diabetes (years) = (Date of informed consent – date of diagnosis of diabetes +1)/365.25.

Age at onset of diabetes (years) = (Date [DD-MM-YYYY] of diagnosis of diabetes – date [DD-MM-YYYY] of birth +1) /365.25. In case of unavailable date of birth, only the year of the date of diabetes diagnosis and the year of the date of birth (retrieve using the age recorded at screening) will be considered in the age at onset calculation.

Duration of previous mealtime insulin treatment (years) = Duration of mealtime insulin treatment in patient life (years) = (Date of informed consent – Date of first intake of mealtime Anti-hyperglycemic therapy in patient life $\pm 1/365.25$.

Duration of basal insulin treatment (years) = (Date of informed consent – Date of first intake of Basal Anti-hyperglycemic therapy $\pm 1/365.25$

HbA1c conversion

IFCC in mmol/mol = $(10.93 \times \text{NGSP in \%}) - 23.5$

Renal function formulas

Creatinine clearance (CLcr) value will be derived using the equation of Cockroft and Gault, using weight assessed at the same visit:

• For Male:

CLcr (mL/min) = $[(140 - age(years)) \times weight(kg)]/$ [0.814 x serum creatinine (μ mol/L)]

• For Female: result above multiplied by 0.85.

GFR will be derived using MDRD formula:

GFR (mL/min/1.73m2) = $\begin{bmatrix} 175x \text{ Serum Creatinine (mg/dL)} & -1.154 \text{ x Age} & -0.203 \text{ x 1.212 (if black)} \\ x 0.742 \text{ (if female)} \end{bmatrix}$

2.5.2 Data handling conventions for efficacy variables

James-Stein shrinkage derivation for subgroup by type of comparator (7)

Overall treatment effect estimator:

$$\hat{\delta}_0 = \frac{\hat{\delta}_1 / \hat{\sigma}_1^2 + \hat{\delta}_2 / \hat{\sigma}_2^2}{1 / \hat{\sigma}_1^2 + 1 / \hat{\sigma}_2^2} \text{ where }$$

 $\hat{\delta_i}$ is the sample difference estimator between both treatment arm obtained in subgroup i.

 $\hat{\sigma}_i^2$ is the variance estimator for subgroup i.

James-Stein shrinkage estimator for subgroup i:

$$\vec{\delta}_i = \hat{c}\hat{\delta}_i + (1-\hat{c})\hat{\delta}_0 \text{ where}$$

$$c = \frac{(\delta_1 - \delta_2)^2 / (\sigma_1^2 + \sigma_2^2)}{2 + (\delta_1 - \delta_2)^2 / (\sigma_1^2 + \sigma_2^2)} \text{ assuming a common } c \text{ for all subgroups } (c_1 = c_2),$$

and by replacing δ_i with $\hat{\delta}_i$ and σ_i^2 with $\hat{\sigma}_i^2$ in the calculation of c.

For any specific c:
$$\operatorname{var}(\breve{\delta}_1) = \frac{1/\sigma_1^2 + 2c/\sigma_2^2 + (1-c)^2/\sigma_2^2 + c^2\sigma_1^2/\sigma_2^4}{(1/\sigma_1^2 + 1/\sigma_2^2)^2}$$

and by replacing σ_i^2 with $\hat{\sigma}_i^2$ in the calculation of the variance.

2.5.3 Missing data

For categorical variables, patients with missing data are not included in calculations of percentages unless otherwise specified. When relevant, the number of patients with missing data is presented.

Derived variables are considered missing if the original variables required to calculate them are missing unless otherwise specified. For example, if either a baseline assessment or an endpoint assessment is missing for a particular patient, then the change from baseline at endpoint is missing. Depending upon the assessment, analyses may not include all patients in the analysis population, because certain patients in the intended population may have missing data.

Handling of computation of treatment duration if investigational medicinal product end of treatment date is missing

For the calculation of the treatment duration, if the date of last IMP administration is missing, the exposure duration should be left as missing.

For the main 6-month on-treatment period, the date of the last IMP administration will be defined as: date of last administration reported on the end-of-treatment e-CRF page or date of Week 26 visit, whichever comes earlier. If the date of Week 26 visit is missing, the date of the last IMP administration will be defined as date of last administration reported on the end-of-treatment e-CRF page or date of randomization visit + 185 days, whichever comes earlier.

For the 12-month on-treatment period, the date of the last IMP administration will be defined as the date of last administration reported on the end-of-treatment e-CRF page.

The last dose intake should be clearly identified in the case report form and should not be approximated by the last returned package date.

Handling of medication missing/partial dates

No imputation of medication start/end dates or times will be performed. If a medication date or time is missing or partially missing and it cannot be determined whether it was taken prior or concomitantly, it will be considered a prior, concomitant, and posttreatment medication.

Handling of adverse events/hypoglycemia with missing or partial date/time of onset

Missing or partial adverse event / hypoglycemia onset dates and times will be imputed so that if the partial event onset date/time information does not indicate that the event started prior to treatment or after the on-treatment period, the event will be classified as treatment-emergent. No imputation of event end dates/times will be performed. These data imputations are for categorization purpose only and will not be used in listings. No imputation is planned for date/time of event resolution.

Handling of adverse events/hypoglycemia when date and time of first IMP administration is missing

When the date and time of the first IMP administration is missing, all adverse events / hypoglycemia that occurred on or after the day of randomization should be considered as treatment-emergent. The exposure duration should be kept as missing.

Handling of hypoglycemia classification when some classification items are missing

Rule for handling missing data in classification items for hypoglycemia will be provided in ADaM metadata.

Handling of missing assessment of relationship of adverse events to investigational medicinal product

If the assessment of the relationship to IMP is missing, then the relationship to IMP has to be assumed and the adverse event considered as such in the frequency tables of possibly related adverse events, but no imputation should be done at the data level.

Handling of potentially clinically significant abnormalities

If a patient has a missing baseline he will be grouped in the category "normal/missing at baseline."

For PCSAs with 2 conditions, one based on a change from baseline value or a normal range and the other on a threshold value, with the first condition being missing, the PCSA will be based only on the second condition.

For a PCSA defined on a threshold and/or a normal range, this PCSA will be derived using this threshold if the normal range is missing; eg, for eosinophils the PCSA is > 0.5 GIGA/L or >ULN if ULN ≥ 0.5 GIGA/L. When ULN is missing, the value 0.5 should be used.

Measurements flagged as invalid by the laboratory will not be summarized or taken into account in the computation of PCSA values.

Handling of missing data in the calculation of HbA1c responders

For HbA1c responders (defined by HbA1c<7%), patients without any available assessment at endpoint (Week 26 for the main 6-month period, and Week 52 for the 12-month period) will be treated as failures (non-responders) in the analysis.

Handling of missing data in the calculation of 7-point SMPG variables

For a given 7-point SMPG profile, at least 5 available measurements will be required to take the profile into account in the statistical analyses (including descriptive analyses at each time-point).

For each profile with at least 5 available measurements, the mean 24-hour plasma glucose concentration and the postprandial plasma glucose excursions will be calculated.

At a given visit, the mean 24-hour plasma glucose concentration analyzed will be the average of the mean 24-hour plasma glucose concentrations (as previously calculated) available in the week before the visit. No minimum number of available mean 24-hour plasma glucose concentrations will be required. The same will apply to the postprandial plasma glucose excursions and to the values at each time-point.

Handling of missing data in the calculation of insulin doses

The daily mealtime insulin dose will be calculated as the sum of the mealtime insulin doses collected on the same day. At least 3 available mealtime insulin doses and no more than 1 snack will be required to calculate the daily mealtime insulin dose.

The daily total insulin dose will be calculated as the sum of the daily basal and daily mealtime insulin doses. If one of the daily insulin doses is missing (basal or mealtime), the daily total insulin dose will not be calculated.

At baseline, daily insulin doses (basal, mealtime, and total) will be calculated as the median of the daily insulin doses (as previously calculated) available in the 7 days before the day of first IMP. At Visit 3, daily insulin doses (basal, mealtime, and total) will be calculated as the median of the daily insulin doses (as previously calculated) available in the 7 days after the day of first IMP. At further visits, the daily insulin doses (basal, mealtime, and total) will be calculated as the median of the daily insulin doses (basal, mealtime, and total) will be calculated as the median of the daily insulin doses (basal, mealtime, and total) will be calculated as the median of the daily insulin doses (as previously calculated) available in the 7 days before the visit. No minimum number of available doses will be required. For insulin doses in U/kg, if the body weight measurement is missing at a given visit, the last available measurement from previous visit will be used.

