Patients with T1DM or T2DM (T2DM US only) on a MDI regimen are eligible for the study. The clinical data that support the diagnosis of T1DM or T2DM are placed into the source documentation prior to randomization. Antibodies such as glutamic acid decarboxylase (GAD) antibodies or C-peptide levels may be supportive but are not alone considered diagnostic of T1DM, and in this trial are not assessed at screening. Patients with late onset T1DM are not excluded from the study. The diagnosis of T2DM will be based on the medical history, including high blood glucose levels caused by a lack of insulin and/or insulin resistance, with an onset most often in middle-aged and older adults. Common co-morbidities include obesity, hypertension, and hyperlipidemia. Insulin is typically initiated when diet and life-style changes, followed by add-on metformin and other oral antihyperglycemic drugs, have failed. The exclusion criteria in this trial based on the pre-trial basal and rapid-acting insulin include: use of an insulin pump in the

13-Dec-2017 Version number: 1

3 months before screening visit, use of basal insulin other than insulin glargine in the 6 months before screening visit or insulin detemir in the 12 months before screening visit and use of rapid-acting insulin other than Novolog/NovoRapid or insulin lispro in the 6 months before screening visit.

The dose of SAR341402/NovoLog/NovoRapid will be adjusted at each meal and snack ("meal or snack" will be hereafter referred to as "meal") by the patient based on the pre-meal SMPG and an assessment of the carbohydrate content of the meal (when available). Changes in activity may also be taken into account.

SAR341402/NovoLog/NovoRapid will be injected SC immediately (within 5 to 10 minutes) before meal intake. Occasional postprandial injection soon after meal intake may be done if deemed necessary and if allowed by the national product label for NovoLog/NovoRapid.

Lantus will be injected SC once daily. The dose of Lantus is to be optimized based on the fasting (prebreakfast) SMPG, and with the titration goal being an SMPG of 4.4 to 7.2 mmol/L (80 to 130 mg/dL), while avoiding hypoglycemia.

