8.1.6 Evaluation of patients not meeting glycemic goals

In addition to the scheduled SMPG done by patients, central laboratory alerts on FPG and on HbA1c are set up to ensure that glycemic parameters remain below predefined threshold values. There is no specified rescue treatment. The thresholds values are defined as follows:

- From Visit 7 (Week 12) onwards and inclusive to Visit 9 (Week 26): FPG >11 mmol/L (>200 mg/dL) or HbA1c >8.5%.
- In case of FPG or HbA1c above the target values and/or SMPG are not improving as expected in spite of successive insulin dose titration, the Investigator should ensure that no reasonable explanation exists for insufficient glucose control and in particular that:
 - Plasma glucose was actually measured in fasting condition (ie, after at least 8 hours fasting),
 - Rebound hyperglycemia is excluded,
 - IMP dose is properly adjusted,
 - NIMP dose is properly adjusted,
 - Correction doses for pre-prandial glucose values above goal are used by patient,
 - There is no inter-current disease which may jeopardize glycemic control (eg, infectious disease),
 - Compliance to diet and lifestyle is appropriate, in particular, dosage adjustment for changes in carbohydrate content of the meal and SMPG.
- If any of the above can reasonably explain the insufficient glycemic control, the Investigator should undertake appropriate action, ie:
 - Titrate the mealtime insulin dose of IMP,
 - Set up adequate investigation and treatment of inter-current disease (to be reported in AE/SAE/concomitant medication parts of the e-CRF),
 - Stress the absolute need to be compliant to treatment,
 - Stress the importance of consistency in meals and insulin dosing, particularly during this time of poor glycemic control,
 - Monitor night time glucose,
 - Organize a specific interview with a Registered Dietician or other medically qualified person to stress on the absolute need to be compliant to diet and lifestyle recommendations, in particular with attention to awareness of the carbohydrate content of the meal and covering all snacks with a dose of rapid-acting insulin,
 - Schedule a FPG / HbA1c assessment at the next visit.

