9.3.2 Insulin dose

All mealtime insulin doses and the basal insulin dose will be integrated into e-CRF from the e-diary record as follows:

- For the 7 days prior to Baseline (Visit 3) and during the first 7 days after start of IMP.
- For 2 days in the weeks prior to Visit 5 (Week 4), Visit 7 (Week 12), Visit 9 (Week 26), Visit 11 (Week 40) and Visit 12 (Week 52).

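### Read literally, the SAP's daily mealtime dose rule discards fully recorded days with two or more snack doses, and it can bias the descriptive dose summaries in either direction

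*SAP*

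**What the plan says.** SAP 2.5.3, in its rules for missing insulin dose data, builds the dose in three steps.

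- **Day, mealtime:** "The daily mealtime insulin dose will be calculated as the sum of the mealtime insulin doses collected on the same day". The day is used only if it meets this condition: "At least 3 available mealtime insulin doses and no more than 1 snack will be required to calculate the daily mealtime insulin dose".
- **Day, total:** "If one of the daily insulin doses is missing (basal or mealtime), the daily total insulin dose will not be calculated". A rejected mealtime day is therefore also a lost total-dose day.
- **Visit:** the value is the median of the usable days in the relevant week, and "No minimum number of available doses will be required".

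The SAP does not say whether the snack is one of the three doses, whether all three main meals must be present, how correction doses count, or why a day with several snack doses cannot be used.

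On conduct, Protocol 6.1 states: "The dose of SAR341402/NovoLog/NovoRapid will be adjusted at each meal and snack". The same sentence then defines a meal to include a snack. For patients not meeting glycemic goals, Protocol 8.1.6 includes "covering all snacks with a dose of rapid-acting insulin" in the dietary advice. Protocol 9.3.2 collects doses on seven days before baseline and seven days after the start of treatment, but on only two days before each later visit.

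**The concern.** The condition sits among the missing-data rules, yet one half of it rejects days on which nothing is missing. Days with several snack doses are an expected result of following the protocol. They may be more common in patients with poor control, because Protocol 8.1.6 advises those patients to cover all snacks and its laboratory alerts run from Week 12 to Week 26. Loss of data could then depend on glycemic control and on time since baseline, and would not necessarily cancel in a change from baseline.

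The other half is weak as a completeness check. If a snack counts among the three doses, a day without one main-meal dose passes, and nothing shows whether that dose was skipped or not recorded.

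The variable feeds the exposure summaries (SAP 2.4.3.1) and several antibody outputs (SAP 2.4.5.7): dose change by antibody status, peak titer against change in total dose, and doses by category of HbA1c change. In an open-label trial with self-titration to glucose targets, dose helps to interpret similar HbA1c results.

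**Working it through.** The plan states no figure for this rule, so there is none to reproduce. The check has three parts.

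**1. Which days pass.** Let *m* be the number of recorded main-meal doses and *s* the number of recorded snack doses. Three readings are possible:

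- A (literal): m + s ≥ 3 and s ≤ 1.
- B (at most one of the three qualifying doses is a snack; further snacks allowed): m + min(s, 1) ≥ 3.
- C (three main meals, and no more than one snack): m = 3 and s ≤ 1.

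The sums assume 8 U per main meal and 3 U per snack. These values are not in the documents.

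| m + s | Sum (U) | A | B | C |
|---|---|---|---|---|
| 2 + 0 | 16 | reject | reject | reject |
| 2 + 1 | 19 | accept | accept | reject |
| 2 + 2 | 22 | reject | accept | reject |
| 3 + 0 | 24 | accept | accept | accept |
| 3 + 1 | 27 | accept | accept | accept |
| 3 + 2 | 30 | reject | accept | reject |
| 3 + 3 | 33 | reject | accept | reject |

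Reading A drops the highest-dose days and accepts a day without one main-meal dose. All three readings drop the low-dose 2 + 0 day.

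**2. Bias in the mean dose of accepted days.** Bias = (mean recorded dose on accepted days ÷ true mean dose) − 1. Further assumptions: snacks per day are Poisson with mean λ, each main-meal dose is skipped with probability k, and each dose taken goes unrecorded with probability u.

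With k = u = 0, Reading A has a closed form, because the mean number of snacks on days with at most one is λ/(1 + λ):

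- λ = 0.7: true mean 24 + 3 × 0.7 = 26.1 U; accepted mean 24 + 3 × 0.7/1.7 = 25.24 U; bias −3.3%.
- λ = 1.5: true mean 24 + 3 × 1.5 = 28.5 U; accepted mean 24 + 3 × 1.5/2.5 = 25.8 U; bias −9.5%.

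Selected results by exact enumeration:

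| λ | k | u | True mean (U) | A | B | C |
|---|---|---|---|---|---|---|
| 0.7 | 0 | 0 | 26.1 | −3.3% | 0.0% | −3.3% |
| 1.5 | 0 | 0 | 28.5 | −9.5% | 0.0% | −9.5% |
| 0.7 | 0 | 0.1 | 26.1 | −6.3% | −3.8% | −3.6% |
| 1.5 | 0 | 0.1 | 28.5 | −13.5% | −6.2% | −9.7% |
| 0.3 | 0.1 | 0 | 22.5 | +7.9% | +8.7% | +9.7% |
| 0.7 | 0.1 | 0 | 23.7 | +3.3% | +6.5% | +6.5% |
| 1.5 | 0.1 | 0 | 26.1 | −5.5% | +3.9% | −1.1% |
| 0 | 0.2 | 0 | 19.2 | +25.0% | +25.0% | +25.0% |

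The grid covered λ of 0, 0.3, 0.7 and 1.5, k up to 0.2 and u up to 0.1. Its extremes were −13.5% and +25.0%. Every reading can overstate and can understate.

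**3. Loss of whole visits under Reading A.** With k = u = 0, a day is kept with probability e^(−λ)(1 + λ), which is 0.844 at λ = 0.7 and 0.558 at λ = 1.5. If days were independent, both days of a later visit would be lost with probability (1 − 0.844)² ≈ 2.4% and (1 − 0.558)² ≈ 20%. At baseline with seven days and λ = 1.5, the figure is (1 − 0.558)⁷ ≈ 0.3%. Snacking habits persist within a patient, so independence is optimistic. A patient who doses two snacks every day has no usable day.

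**The case against.** The strongest reply is that the sentence is a completeness minimum. Since Protocol 6.1 counts a snack as a meal, it can sensibly mean that no more than one of the three qualifying doses may be a snack. That is Reading B, which drops no three-meal day. The reply is fair, but the wording does not settle the matter, and a programmer applying it as written would code the limit.

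A reader might also infer that insulin doses are understated however the rule is read. The documents do not support that:

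- The three-dose minimum removes genuine low-dose days, which pushes the summary up.
- An absent main-meal dose may not have been taken, and then the recorded sum is correct.
- Reading B has no bias when every dose is taken and recorded.
- Reading C accepts no day that lacks a main-meal dose.

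Two further replies stand in part. The same rule applies in both arms and at all times, so a common shift would largely cancel unless snack dosing differs by arm or over time. The documents do not show a difference by arm; the advice in Protocol 8.1.6 makes a change over time possible but does not establish it. Also, insulin dose is listed among other endpoints (Protocol 9.3.2), and no hypothesis test uses it.

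**Conclusion.** The point holds as an ambiguous and, read literally, selective acceptance rule. It rejects complete days with two or more snack doses, accepts two main meals plus a snack, and carries each rejection through to the daily total, with only two collection days at later visits. It can bias the dose and dose-versus-antibody summaries in either direction.

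The range of −13.5% to +25.0% is illustrative. It rests on assumed unit doses, snack frequency, skipping and non-recording, and it concerns the mean of accepted days, whereas the plan takes a median per patient and visit. The documents give none of these rates, so neither size nor sign can be fixed. The primary endpoint is unaffected. This is a minor point that is worth correcting because the main part of the correction is nearly free.

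**What to change.** In SAP 2.5.3:

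1. Delete the upper limit on snacks. On any day that meets the completeness minimum, sum all recorded mealtime, snack and correction doses.
2. Define the minimum on the main meals (breakfast, lunch and dinner). Count a skipped meal as zero only where the e-diary or e-CRF identifies the dose as not taken.

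The documents do not say whether a dose not taken can be told from one not recorded, and randomization began on 14-Aug-2017, before this SAP (28-Feb-2018). If that information is not captured, step 2 would lose some two-meals-plus-snack days that are now accepted. In that case make only the snack change, worded so that at most one of the three qualifying doses may be a snack and further snacks do not disqualify the day. Simply striking the snack phrase would let through a day with one main meal and two snacks.

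The cost is one or two sentences in the SAP and an edit to the derivation. No dosing instruction or data collection changes.

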2.5.4 Windows for time points

The following process will be applied for visit re-allocation. Re-allocated visits will be used in all statistical analyses (descriptive statistics, plots, and statistical models).

No re-allocation will be performed for nominal visits already provided in the clinical database (Visit 1 to Visit 13), and for unscheduled assessments.

SMPG profiles and insulin doses

In the clinical database, SMPG profiles and insulin doses transferred from the e-diary will not be assigned to a protocol visit. For the analysis, they will be assigned to the next on-site visit actually performed by the patient after the date of data collection (Visit 3 to Visit 12, or Visit 8000).

End of treatment visit

If a patient discontinues the treatment prematurely, end of treatment (Visit 8000) assessments will be re-allocated to the next scheduled on-site visit for the patient. The next scheduled on-site visit for each patient will be determined as the next on-site visit that should be performed as per protocol, following the last visit actually performed by the patient before Visit 8000.

For a given parameter, the value will not be re-allocated in the following cases:

- If the parameter is not planned to be collected at the re-allocation visit.
- If a value is already available for the parameter at the re-allocation visit.

This process will be used to retrieve all assessments (including efficacy, safety, and immunogenicity data) performed at the end of treatment visit (Visit 8000), and will apply to insulin doses assigned to Visit 8000 following the process described above.

